Several instruments have been widely used in quality of life research, including the 36-Item Short Form Health Survey (SF-36), the 12-Item Short Form Health Survey (SF-12), the World Health Organization Quality of Life Instruments (WHOQOL-BREF), EuroQoL-5D (EQ-5D-5L) and the Short-Form Six-Dimension (SF-6D). Our team has experience using the SF-36, SF-12v2(HK) and the EQ-5D-5L survey instruments for monitoring quality of life in research subjects in Hong Kong. For example, we found that trauma patients in Hong Kong scored significantly worse on the SF-36 twelve months after injury.¹⁷ We also found the most dramatic improvements happened in the first one to six months post-injury,¹⁹ and that 45% of subjects had achieved an excellent outcome by four years post-injury.²⁰ The SF-12v2(HK) with four week recall is a modified version of the SF-36 to be shorter and quicker to use, while also already translated and validated in Hong Kong.²¹ We aim to combine our experience with conducting quantitative quality of life studies with the CUHK Department of M&T's expertise in coronavirus treatment and follow-up to explore the quality of life of COVID-19 patients in recovery.

The reported mortality rates for COVID-19 has so far been lower than SARS, although the higher absolute numbers of COVID-19 patients mean worldwide deaths are overall much higher. Trauma, sepsis and SARS survivors have all experienced significant long-term morbidity and decreased quality of life as a result of their injuries or infections. A previous study of patients infected with SARS-CoV-1 in 2003 at PWH showed that significant numbers of recovering patients had impaired long-term health status.¹² The question this study hopes to answer is to what degree do COVID-19 patients suffer a similar fate? Has the knowledge gained from the SARS experience led to improved quality of life outcomes compared to SARS survivors? Or do the similarities between the viruses that cause SARS and COVID-19 extend to a reduced quality of life after recovery as well?

Aims

This study aims to determine the quality of life of COVID-19 survivors up to six-months after discharge from hospital or quarantine. We also aim to compare the quality of life of COVID-19 survivors to baseline known Hong Kong quality of life norms.

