After written consent is obtained, the pre-COVID-19 and baseline information will be collected. Their COVID-19 information will be collected via face-to-face interview or telephone follow-up or by email. 1, 3 and 6-month data post-discharge will be collected via telephone follow-up interview with the patient or e-form completed by the patient.

Quality of life assessment tools

SF-12

The 12-Item Short Form Health Survey is an abbreviated version of the 36-Item Short Form Health Survey. It is a widely used, international, validated survey for investigating health-related quality of life in a variety of both acute and chronic conditions. The survey instrument has eight domains: physical functioning, physical role, bodily pain, general health, vitality, social functioning, emotional role, and mental health. Each domain is measured on a 0-100 scale. A higher score correlates with a higher quality of life. The survey generates a Mental Component Summary (MCS) and a Physical Component Summary (PCS). A Chinese version of the survey, the 12-item Chinese (Hong Kong) Short Form Health Survey (version 2) (SF-12v2 (HK)) has been previously validated and used in Hong Kong.²¹ We will be using the four week recall (standard) version of the SF012v2(HK).

EQ-5D-5L

The EQ-5D-5L is a brief health status measure that comprises of five domains: mobility, self-care, pain, usual activities, and psychological status. EQ-5D-5L has been validated in Hong

Kong, recently for use in patients with chronic obstructive pulmonary disease.²³

Return to work status

Patients' pre-COVID-19 infection work status will be compared to their post-infection status. The type of employment, salary and each patients' subjective work experiences before and after infection will be queried.

Definitions

COVID-19 = Coronavirus Disease 2019, the new disease pandemic caused by the SARS-CoV-2 virus.

CUHK = The Chinese University of Hong Kong

EQ-5D-5L = EuroQol Five Domain survey, one of the two main survey instruments we will use to quantitatively judge quality of life for enrolled study subjects.

NTEC = New Territories East Cluster, a grouping of healthcare facilities in northeast Hong Kong.

PWH = Prince of Wales Hospital, the largest acute care hospital in the Hong Kong Hospital Authority's New Territories East Cluster as well as the major teaching hospital for the Chinese University of Hong Kong's medical school.

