SARS = Severe Acute Respiratory Syndrome, the disease associated with the coronavirus epidemic of 2003 (not to be confused with SARS-CoV-2, which is the virus causing COVID-19 disease).

SARS-CoV-2 = Severe Acute Respiratory Syndrome Coronavirus 2, the virus identified as the causative organism of the COVID-19 disease.

SF-12 = The 12-Item Short Form Health Survey, one of the two main survey instruments we will use to quantitatively judge quality of life for enrolled study subjects. We will use the SF-12v2(HK) version of the SF-12, which has been specifically validated for use in Hong Kong.

Study design

Recruitment

All adult COVID-19 patients aged ≥ 18 years who present to the infectious diseases specialist outpatient follow-up clinic at PWH will be screened for inclusion in this study by research assistants involved in this study.

First interview

After consent, the pre-COVID-19 assessments of SF-12v2(HK) and EQ-5D-5L will be obtained

by face-to-face interview or by phone interview by a research assistant or by e-form completed by the patient. The interview process should take no longer than 10 minutes. The questionnaire may be completed by a proxy if the patient is unable to respond to the interviewer. Work status one month prior to COVID-19 diagnosis will be determined at this time as well.

Follow-up interviews

The SF-12v2(HK) and EQ-5D-5L will be obtained by telephone interview from the patient or e-form completed by the patient. The follow-up measures will be performed at 1, 3, and 6-months after date of recovery by a research assistant.

Studies have found differences between quality of life assessments completed by the patient or by proxy. In previous studies, it has been shown that when using EQ-5D-5L as an assessment tool, there is good agreement on the domain of self-care, but only a “fair” agreement on domains such as mobility, pain and anxiety were observed between the patients and caregiver rating.²⁴ However, if all proxy responses were excluded, quality of life for survivors of sepsis with communication problems would not be included, which would be a significant methodological and ethical problem. Thus, in this proposed study, the questionnaire may be completed by a proxy if the patient is unable to respond to the interviewer (e.g. patients with dementia or stroke). A subgroup analysis will be performed accordingly.

Data processing and analysis

Outcomes

Primary outcome

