COVID-19 is still an incompletely understood disease. We will perform secondary analyses on the data to allow us to focus on specific groups and to adjust for variability. We will consider the severity of COVID-19 by examining each patient's clinical record, number of hospital days admitted, number of days spent in the intensive care unit, number and severity of organ(s) dysfunction, co-infections, pathogen(s) identified, pre-COVID-19 health status and pre-existing conditions. It is anticipated that there will be marked changes and differences in health status and functional outcome depending on patient age. Comparisons of quality of life between four time points (pre-sepsis, hospital stay, 3-months and 6-months after discharge) will be assessed using paired t-test or Wilcoxon (W) tests as appropriate.

Multivariate logistic regression analysis

All parameters will be entered into a multiple logistic regression model and used to evaluate associations and account for variation. Multiple logistic regression adjusts for variable interactions and will be used to identify predictors of quality of life in COVID-19 patients during follow-up.

References

1. World Health Organization. *Situation Report-78 HIGHLIGHTS.*; 2020. https://www.who.int/docs/default-source/coronavirus/situation-reports/20200407-sitrep-78-covid-19.pdf?sfvrsn=bc43e1b_2. Accessed April 10, 2020.
2. Centre for Health Protection of the Department of Health of the Hong Kong SAR. *Countries/Areas with Reported Cases of Coronavirus Disease-2019 (COVID-19).*; 2020. https://www.chp.gov.hk/files/pdf/statistics_of_the_cases_novel_coronavirus_infection_en.pdf. Accessed April 10, 2020.
5. Hui DS. Severe acute respiratory syndrome (SARS): Lessons learnt in Hong Kong. *J Thorac Dis.* 2013;5(SUPPL.2). doi:10.3978/j.issn.2072-1439.2013.06.18

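### The time points in the secondary comparison do not match the questionnaire schedule: the 1-month round is left out and a hospital-stay point with no described questionnaire is listed

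*Combined protocol and SAP*

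**What the plan says.** **Collection.** At the first interview, "After consent, the pre-COVID-19 assessments of SF-12v2(HK) and EQ-5D-5L will be obtained". For follow-up, the Methods section says "1, 3 and 6-month data post-discharge will be collected via telephone follow-up interview with the patient or e-form completed by the patient", and Study design, Follow-up interviews, says "The follow-up measures will be performed at 1, 3, and 6-months after date of recovery by a research assistant". The time origin is worded differently (discharge in one, recovery in the other), but the three intervals are the same. Both instruments are used each time: "The SF-12v2(HK) and EQ-5D-5L will be obtained by telephone interview from the patient or e-form completed by the patient".

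**Analysis.** Statistical analysis, Secondary analyses, names four time points: "Comparisons of quality of life between four time points (pre-sepsis, hospital stay, 3-months and 6-months after discharge) will be assessed using paired t-test", with the Wilcoxon test as the alternative. No other analysis names the 1-month round. The primary analysis is at six months, and the logistic regression refers only to follow-up in general. The plan gives no repeated-measures model, missing-data method, dropout rate or multiplicity adjustment.

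**The concern.** The Aims section asks about quality of life up to six months after discharge, so the 1-month questionnaire belongs to the stated question. The SF-12v2(HK) form has a four-week recall. The 1-month form therefore covers roughly the first month after discharge, and a 3-month form cannot recover that period. An analyst who follows the list literally would make no comparison involving 1 month and would look for hospital-stay scores that no section says are collected. Any 1-month contrast reported later would be unplanned and open to the criticism that it was chosen after the data were seen.

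A second, conditional issue is the choice of test. A paired test uses only patients with both questionnaires. If some are missed, the contrasts can describe different sets of people, and patients with an early score but no later one drop out of the later contrast. When dropout depends on earlier scores, this can distort the estimated change.

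**Working it through.** **1. Time points side by side**

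| Time point | Questionnaire described? | In the analysis list? |
|---|---|---|
| Pre-COVID-19 | Yes (First interview) | Yes, but worded as pre-sepsis |
| Hospital stay | No | Yes |
| 1 month | Yes | No |
| 3 months | Yes | Yes |
| 6 months | Yes | Yes |

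Screening takes place at an outpatient follow-up clinic and the first interview records the pre-COVID-19 state. The Methods section mentions baseline information without defining it, but nowhere describes a questionnaire about the hospital stay.

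**2. Contrasts**

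- Collected points: 4, so 4 × 3 / 2 = 6 pairs.
- Planned and feasible: pre–3, pre–6 and 3–6, which is 3 of 6.
- Collected but not planned: pre–1, 1–3 and 1–6, which is 3 of 6.
- Planned but with no described questionnaire: the 3 pairs involving hospital stay.
- At the 100 patients given in Methods, with full response, 100 of 400 scheduled questionnaire rounds enter no stated time-point comparison.

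**3. Would a 1-month contrast be informative?** The documents give no SD or correlation. I assume SD 10 and within-patient correlation ρ of 0.5 to 0.7, with n = 100 complete pairs.

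- SD of change = 10 × √(2(1 − ρ)): 10.0 at ρ = 0.5 and 7.75 at ρ = 0.7.
- 95% half-width = 1.96 × SD of change / √100: 1.96 and 1.52 points.
- Change detectable with 80% power = 2.80 × SD of change / √100: 2.80 and 2.17 points.

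On these assumptions the omitted contrasts would be estimated to within about 1.5 to 2.0 points.

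**4. Do the paired tests use different patients?** No missingness rate is stated, so these are assumed rates with N = 100.

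| Assumed missingness | pre–3 | pre–6 | 3–6 |
|---|---|---|---|
| None | 100 | 100 | 100 |
| 10% per follow-up, independent | 90 | 90 | 81 |
| 10% per follow-up, monotone | 81 | 73 | 73 |
| 20% per follow-up, independent | 80 | 80 | 64 |
| 20% per follow-up, monotone | 64 | 51 | 51 |

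With q the retention per visit, independent losses give Nq, Nq and Nq². Monotone losses give Nq², Nq³ and Nq³. With no missing data all contrasts share the same patients. Under monotone dropout, pre–6 and 3–6 use the same patients and only pre–3 differs.

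**5. Can the paired change be biased?** This is an illustrative simulation. The assumed means are 50, 44, 47 and 49, so the true pre-to-6-month change is −1.00, with SD 10. Loss of the 6-month score is more likely at lower 1-month scores (log-odds 0.08 per point).

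| Six-month scores lost | Paired, pre–post correlation 0.4, post–post 0.6–0.7 | Using pre and 1-month scores, same correlations | Paired, all correlations 0.6 |
|---|---|---|---|
| 10% | −0.85 | −1.00 | −1.00 |
| 20% | −0.72 | −1.00 | −0.99 |
| 30% | −0.57 | −1.00 | −0.99 |

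Bias appears when post-illness scores correlate more strongly with each other than with the pre-COVID-19 score. It is essentially absent when all correlations are equal.

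**6. Multiplicity.** The plan tests at 0.05 without adjustment. Three feasible contrasts on two summary scores make 6 tests, and 1 − 0.95⁶ = 26.5% if independent. Five contrasts on two scores make 10 tests, and 1 − 0.95¹⁰ = 40.1%. Adding 1-month contrasts therefore needs a statement on multiplicity.

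**The case against.** The strongest reply is that this is a wording slip in a secondary analysis. The primary and secondary outcomes are all at six months, paired tests are valid for complete pairs, and nothing forbids reporting 1-month scores under the general t-test provision or the regression on follow-up. Much of this stands. A reader might infer that the study cannot report 1-month results, but the documents support only the narrower statement that no 1-month contrast is prespecified.

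Three other inferences also go too far.

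- *Early recovery is never tested.* The list nominally includes hospital stay against 3 months, which spans early recovery. That contrast fails because no hospital-stay questionnaire is described.
- *Every contrast rests on a different subset, so results are biased and imprecise.* This depends on missingness that the documents do not give. With complete data it is untrue, and under monotone dropout it is only partly true. The precision gain from a joint model was modest in simulation, at 0 to 11% of the standard error with an assumed 67–72% of patients having a six-month score. Preferring a mixed model on that ground alone is a choice of efficiency.
- *The team's own data show that 1 month is where recovery begins.* The background states "We also found the most dramatic improvements happened in the first one to six months post-injury", but this concerns trauma patients timed from injury. It makes interest in early recovery reasonable and does not establish the course after COVID-19 discharge.

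What survives the objection is the mismatch itself, which needs no assumption.

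**Conclusion.** The mismatch is certain and follows from reading the sections together. One scheduled round is missing from the analysis list, one listed point has no described questionnaire, and one label belongs to another disease. As written, 3 of the 6 contrasts among collected points are prespecified and the 3 involving 1 month are not. Removing hospital stay from the list would not cure this, because 1 month would still be absent.

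The point about paired tests holds only conditionally. It matters if questionnaires are missed, and bias further requires that dropout depends on earlier scores and that the correlations are unequal. Its size cannot be stated from the documents. The simulated figures above show that it can range from nil to a substantial share of a small change.

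The list should be corrected before analysis. The six-month outcomes do not depend on it.

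**What to change.** In Statistical analysis, Secondary analyses:

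1. Restate the time points as pre-COVID-19, 1, 3 and 6 months. Drop hospital stay, since no questionnaire is described for it, and replace pre-sepsis.
2. Analyse PCS and MCS, and an EQ-5D-5L score if one is derived, each in a linear mixed model with visit as a categorical factor and an unstructured within-patient covariance. Use all available scores and state the missing-at-random assumption.
3. Name a small set of contrasts with 95% confidence intervals: 1, 3 and 6 months against pre-COVID-19, 1 to 3 months, and 1 to 6 months. Label them descriptive, or secondary with a stated multiplicity adjustment.
4. Keep the paired t-test or Wilcoxon test as a complete-pair sensitivity analysis.
5. Report the number of patients contributing at each visit and to each paired contrast.

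The cost is a change of wording and slightly more analysis, with no new patients, visits or questionnaires. The downsides are more contrasts to report and reliance on missing at random. The paired tests do not verify that assumption, so agreement between the two analyses should not be presented as proof of it.

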The primary outcome measure will be the health summary scores from SF-12v2(HK) in COVID patients at six-months post-discharge from hospital.

Secondary outcomes

The secondary outcome measures will include the health status measures of the EQ-5D-5L and return to work status in COVID patients at six-months post discharge from hospital.

Other measures

The required clinical data for patient characteristics and data for investigating each patient’s relative illness severity will be collected at the earliest opportunity after subject enrollment. The final COVID-19 diagnosis and any other final diagnoses will be recorded from the patient’s existing clinical notes. The Hospital Authority’s computerized Clinical Management System (the

system used by all hospitals under Hospital Authority for storing and retrieving patients' data) will be reviewed to identify hospital admissions, emergency department reattendance, lengths of stay (intensive care, step-down units or general wards) and mortality.

Statistical analysis

General

Chi-square and Fisher's exact tests will be used for categorical data while t-tests will be used to compare means of continuous variables. A p value <0.05 will be considered statistically significant and all tests will be two-tailed.

Primary analysis

A univariate and multivariate analysis of the data set will be conducted at six months. SF-12v2 dimensions of survivors of COVID-19 will be compared with data from past survivors of SARS infection, sepsis or trauma. We will also compare this data to the general Hong Kong population summary score data. Data from the EQ-5D-5L survey instrument will be compared using the Chi-square or Fisher's exact tests.

Secondary analyses

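### The logistic model for predictors of quality of life names no dependent variable, time point or cut-off, although the SF-12v2(HK) summary scores are numeric and could be modelled as such

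*Combined protocol and SAP*

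**What the plan says.** The section on multivariate logistic regression has two sentences. The first is "All parameters will be entered into a multiple logistic regression model and used to evaluate associations and account for variation". The second is "Multiple logistic regression adjusts for variable interactions and will be used to identify predictors of quality of life in COVID-19 patients during follow-up". Neither says which variable is the dependent variable, which follow-up visit is meant, or how quality of life becomes a category.

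The Primary outcome section reads: "The primary outcome measure will be the health summary scores from SF-12v2(HK) in COVID patients at six-months post-discharge from hospital". The SF-12 section describes eight domains scored from 0 to 100 and two summaries, PCS and MCS. Elsewhere the plan treats such data as numeric. The General section uses t-tests for continuous variables, and under Secondary analyses the comparisons of quality of life over time "will be assessed using paired t-test or Wilcoxon (W) tests as appropriate".

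Under Primary analysis the plan also announces a univariate and multivariate analysis at six months, without naming a model. The same section says of the SF-12 data: "We will also compare this data to the general Hong Kong population summary score data". For the other instrument it says "Data from the EQ-5D-5L survey instrument will be compared using the Chi-square" or Fisher's exact test.

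No section defines a poor or good SF-12 category, a threshold based on norms, or an important difference. The excellent-outcome figure in the background comes from the team's earlier trauma work and defines nothing for this study.

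**The concern.** Logistic regression needs a categorical outcome. The plan's main quality-of-life outcome is a pair of numeric scores, and the only regression model that the plan names is logistic. Two statisticians working from this text could fit different models: to PCS, to MCS, to return to work, to an EQ-5D-5L level, at one, three or six months, with any cut.

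Two things follow if the model is applied to PCS or MCS. Splitting a numeric score usually discards information, so real predictors are missed more often. And a cut that is not fixed beforehand can be chosen once the data are seen, so the reported associations depend on that choice.

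Two smaller faults sit in the same sentences. Entering all parameters is not a covariate list. The statement that the model adjusts for interactions is also incorrect unless interaction terms are put into it.

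**Working it through.** The plan gives no event rate, cut-off, effect size or power for this model, so there is no figure of its own to reproduce. The numbers below are an illustration.

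**Inputs from the documents.** Two-sided 0.05 (General). N=100 (Methods) and about 200 (Sample size calculation); both are shown because the two sections differ.

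**Assumptions.** Ten independent terms, since Secondary analyses lists at least eight severity and history items plus age. One true predictor with standardised effect b=0.3 and error SD √(1−0.3²)=√0.91. Cuts at 50%, 30% and 20% of the sample.

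**Step 1: information kept after a cut.** For a normal score cut at proportion p, relative efficiency is φ(z_p)²/[p(1−p)].
- p=0.5: 0.3989²/0.25 = 0.637
- p=0.3: 0.3477²/0.21 = 0.576
- p=0.2: 0.2800²/0.16 = 0.490

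**Step 2: hand check of power.** With 10 terms and an intercept, the linear model has λ = 0.3·√(N−11)/√0.91, and power ≈ Φ(λ−1.96). For the cut score, λ is multiplied by the square root of the efficiency (0.798, 0.759, 0.700).
- N=100: λ=2.967, linear 84%; cut λ=2.367, 2.251, 2.077, giving 66%, 61%, 55%.
- N=200: λ=4.323, linear 99%; cut λ=3.450, 3.280, 3.026, giving 93%, 91%, 86%.

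**Step 3: simulation** (4,000 data sets per setting, logistic Wald test).

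| Score | N | Linear | Logistic, cut 50% | 30% | 20% |
|---|---|---|---|---|---|
| Normal | 100 | 83% | 65% | 61% | 53% |
| Normal | 200 | 99% | 92% | 90% | 84% |
| Left-skewed transform | 100 | 73% | 65% | 61% | 53% |
| Additive error, skewness −2 | 100 | 84% | 87% | 53% | 34% |

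Repeats of the normal N=100 case with fewer data sets gave 84% for linear regression and 67%, 58-61% and 52-53% for logistic regression. The agreement with Step 2 is close. The fourth row shows that the loss is not universal: with strongly skewed error a median cut costs nothing, while a 20% cut costs 84−34 = 50 points.

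**Step 4: does the result depend on the cut?** With a normal score, the significance verdict on the true predictor differs among the three cuts in 43% of studies at N=100 and 20% at N=200. With skewed scores the ranges are 43-59% and 20-42%.

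**Step 5: false positives for an unrelated predictor** (normal score, 3,000 data sets, cuts as above).

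| How the cut is chosen | N=100 | N=200 |
|---|---|---|
| One cut, fixed in advance | 5.4-5.8% (both N) | |
| One cut for the model, favouring the true predictor | 5.9% | 5.5% |
| One cut for the model, smallest p-value | 7.6% | 5.8% |
| One cut for the model, most significant predictors | 10.5% | 10.1% |
| Best of three cuts separately for each predictor | 13.2% | 12.5% |

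Other runs put the last row between 12% and 14%. Linear regression on the uncut score stayed at 4-6%.

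**Cross-check with a single predictor.** With correlation 0.25, power for the uncut score against a median split is 71% against 53% (N=100) and 95% against 81% (N=200). The best of three cuts at the quartiles gives 12-13% false positives.

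**The case against.** The strongest reply is that the plan never says PCS or MCS will be split. Return to work is a secondary outcome and a natural candidate for logistic regression, and EQ-5D-5L levels are already to be compared by tests for categories. This stands as far as it goes: splitting is an inference. But the stated target is predictors of quality of life, return to work is described separately from the quality-of-life instruments, and the outcome is unnamed on any reading.

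Four stronger readings are tempting and are not supported.

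- A reader might infer that false positives will more than double. The plan describes one model with all terms entered together, so one cut would serve every predictor. The rate is then about 6-11%, at worst close to double the single-cut rate (10.5/5.4 = 1.9). More than doubling requires a separate best cut for each predictor.
- A reader might infer that the main result is compromised. The comparison of scores with Hong Kong norms does not use this model.
- A reader might infer that the problem is confined to secondary work. That cannot be settled either, because the multivariate analysis at six months under Primary analysis has no model named and could be this one.
- A reader might infer that advice to practitioners will rest on these predictors. The sentence about evidence-based conclusions, placed just before the Hypotheses, is mainly about differences from local norms. Neither the aims nor the hypotheses mention predictors.

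It is also fair to say that the power loss rests on assumed inputs and depends on the score's distribution. The firm defect is the undefined outcome; the lost power is a likely consequence.

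**Conclusion.** The point holds as a specification gap with a better method at hand. The plan's only named regression model does not fit its numeric primary measures without a split that it does not define, and it states no dependent variable, time point, cut-off or covariate list.

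If PCS or MCS is split, the illustration suggests that power at N=100 falls from about 83% to about 65%, 60% and 52% for cuts at 50%, 30% and 20%, and from 99% to 92%, 90% and 84% at N=200. This assumes a normal score, ten independent terms and a standardised effect of 0.3. If one cut is chosen after the data are seen, the false-positive rate rises to about 6-11%. The documents show room for such a choice and give no sign that one is intended. The change should be made before analysis.

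**What to change.** In the logistic regression section, name the dependent variable and time point of each model.

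- For PCS and MCS, replace logistic regression with linear regression of the numeric six-month scores, using robust standard errors if the scores are skewed.
- Replace all parameters with a short covariate list fixed in advance from the items in Secondary analyses, for example age, pre-existing conditions and one severity measure. The plan itself expects age to matter: "It is anticipated that there will be marked changes and differences in health status and functional outcome depending on patient age".
- Keep logistic regression for defined categorical outcomes such as return to work.
- Treat any binary SF-12 analysis as supportive, with its cut fixed in advance. That removes the choice of cut but not the loss of information.
- Delete the statement about interactions, or name the interaction terms.
- State under Primary analysis whether its multivariate analysis is this model.

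Adjustment for the recalled pre-COVID score, a mixed model over the follow-up visits and a proportional-odds model are optional.

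The cost is wording only, as the scores and covariates are already to be collected. Mean differences replace odds ratios, and fewer covariates are examined at once. Robust standard errors cost a few points of power at N=100: 83% to 79% with a normal score, and 73% to 67% with the skewed transform, where the gain over a median cut shrinks to about 2 points.
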